6.7 Recommended Pre-Procedure Medications

Recommended pre-procedure medications are in accordance with the applicable IFU recommendations:

- **Anticoagulation Therapy**
 Subjects on anticoagulants prior to implant may continue their pre-procedure regimens of anticoagulation at the discretion of the implanting physician. Subjects currently taking anticoagulation for history of stroke or TIA may suspend anticoagulation 3 days prior to the implant procedure, at the investigator’s discretion. If the patient has been on anticoagulation within 7 days of the procedure it is recommended that the patient’s INR is checked within 24 hours prior to implant and that the implant procedure should not be performed if the subject’s INR \geq 2.0.
- **Aspirin Therapy**
 Administration of aspirin one day prior to the procedure is recommended at the physician’s discretion.

	Title: WAVECREST Post Market Clinical Follow-Up (PMCF) Study	Doc. #: CHX_IP015	Rev: D
---	---	-----------------------------	------------------

- **Antibiotic Therapy**

Use of antibiotic for endocarditis prophylaxis prior to the implant procedure is recommended per the site's standard of care.

6.8 Implant Procedure

Follow the Coherex WaveCrest LAA Occlusion System Instructions for Use (IFU) for the implant procedure.

- Perform Implant Procedure
 - Perform a transseptal puncture using standard catheterization methods.
 - A TEE should be performed prior to the procedure to determine if the anatomy is appropriate for implantation and to confirm the absence of thrombus in the LAA
 - Images of the LAA ostium should be taken to confirm minimum and maximum width measurements prior to selecting a device size.
 - The subject should be heparinized to maintain an activated clotting time (ACT) >250 seconds for the duration of the procedure (prior to introduction of the implant and until sheath is withdrawn). Bivalirudin may be used if heparin is contraindicated. ACT measurement is not required if bivalirudin is used. *Note: Bivalirudin should not be used if the INR is >2.0.*
 - Confirm and record the position and stability of the implant using both fluoroscopy and TEE before and after device release.
- Administer recommended post-implant medications per physician's discretion as subject's condition dictates.
- Provide subject with Patient Implant Card (this card will provide the investigator's contact information and device identification number)
- Record antiplatelet and anticoagulant medications
- Record adverse events, device malfunctions and protocol deviations as appropriate

6.9 Discharge

Before the subject is discharged from hospital:

- Administer QVSFS questionnaire
 - If there is any concern for stroke, a visit to the neurologist or physician qualified to perform neurologic assessment is recommended
- Record antiplatelet and anticoagulant medications.
- Record adverse events, device malfunctions and protocol deviations as appropriate.
- Discharge subject on 75-325mg aspirin daily and 75mg clopidogrel.

Table 4 summarizes the post-procedure anticoagulation and antiplatelet regimen.

Note: Subjects who are not implanted with a device should be followed through hospital discharge for adverse events and appropriate CRF to be completed.

	Title:	Doc. #:	Rev:
	WAVECREST Post Market Clinical Follow-Up (PMCF) Study	CHX_IP015	D

6.10 45-Day Office Visit (\pm 15 days)

At the 45-day office visit:

- Perform physical exam (This is referring to the physical examination or ‘check-up’ of the patient for signs of disease or symptoms).
- Study personnel must administer the QVSFS;
 - If QVSFS score $>$ 0, a visit to the neurologist or physician qualified to perform neurologic assessment as soon as possible following QVSFS administration is recommended. The modified Rankin stroke scales should be administered by trained study personnel.
- Perform a TEE following the Echocardiography Protocol.
- If patient has been on anticoagulation, cessation of anticoagulation is at physician discretion provided flow around the implant, with correlate 2D residual gap, is demonstrated on TEE to be \leq 5mm. At the time the subject stops anticoagulation clopidogrel 75mg daily should be started and should continue until 90 days post-implant (prasugrel or ticagrelor may be used in place of clopidogrel, but must not be used with anticoagulation).
- Instruct subject to remain on 75 -325 mg aspirin indefinitely. **Table 4** summarizes the post-procedure anticoagulation and antiplatelet regimen.
- Record antiplatelet and anticoagulant medications.
- Record protocol defined adverse events, device malfunctions and protocol deviations as appropriate.

The schedule of assessments is listed below in **Table 3**.

Table 3: Schedule of Assessments

Assessment	Screening/ Baseline	Treatment Visit (Through discharge)	45 Day Visit \pm 15 days
Medical history	X		
Physical exam*	X		X
Pre-Procedure blood work	X		
CHA ₂ DS ₂ -VASc score	X		
TEE	X	X	X
QVSFS	X	X	X
Antiplatelet and Anticoagulant Medication Review	X	X	X
Adverse Event Monitoring ^a	X	X	X
In case QVSFS $>$ 0 or history of stroke or suspected stroke/TIA			
Neurologic exam ^b	X		X
Modified Rankin Scale	X		X
Brain Imaging (MRI – if contraindicated, then CT)	X ^c		X ^d

^a Adverse event monitoring is initiated upon vascular access with Delivery Sheath.

^b Neurologic visit/exam at baseline for history of stroke or TIA or anytime QVSFS $>$ 0 is recommended, per physician’s judgment

^c Brain imaging results may be collected if imaging is performed as part of routine practice or performed at time of prior stroke (at any time)

^d Brain imaging results may be collected if imaging is performed as part of routine practice

* This is referring to the physical examination or ‘check-up’ of the patient for signs of disease or symptoms

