	
 • Adverse event evaluation • QVSFS Questionnaire 
45 Day Follow-up (± 15 days)
 
 • Physical exam (This is referring to the physical examination or ‘check-up’ of the patient for signs of disease or symptoms) • TEE • Medication assessment • Adverse event evaluation • QVSFS questionnaire
Neurological Assessment	
If there is any concern for stroke (at scheduled visits, QVSFS results in a score > 0), a visit with neurologist or physician certified to assess neurological status is recommended, per physician’s judgment.
 
 • If stroke is suspected and/or confirmed 
 ○ Trained study personnel should administer the Modified Rankin Scale (Appendix IV) ○ Brain imaging (MRI, unless contraindicated, then CT): results may be collected if brain imaging is done as part of routine practice. • If stroke is confirmed, results of appropriate investigations done as part of routine practice, including transesophageal echocardiogram, to determine stroke etiology will be collected.
Medication regimen and Post-Procedure Care	
 • Patients on anticoagulants prior to implant may continue their pre-procedure regimens of anticoagulation at the discretion of the implanting physician • Patients should be advised to use appropriate endocarditis antibiotic prophylaxis for future dental and surgical procedures for at least 6 months post-implant • Patients who are not on anticoagulants should receive clopidogrel 75 mg per day for 90 days post implant • All patients should be maintained on 75 mg - 325 mg of aspirin per day indefinitely except those on anticoagulation. A lower dose aspirin is recommended while patients are on clopidogrel. • Patients should have follow-up visit at 45 days and standard of care imaging, including TEE to assess device position and LAA closure. • Patients should be followed in accordance with recommendations for treatment of atrial fibrillation

	Title: WAVECREST Post Market Clinical Follow-Up (PMCF) Study	Doc. #: CHX_IP015	Rev: D
---	---	-----------------------------	------------------

Contacts:

Sponsor/Manufacturer	Coherex Medical, Inc. [name] USA [contact] Fax:+PPD
PPD	PPD Coherex Medical, Inc. [contact] Fax: +PPD Email: PPD PPD Phone + PPD E-mail: PPD
PPD	PPD Office: PPD Mobile: PPD E-mail: PPD

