6.11 Unscheduled Neurologic Visit

A neurologic visit may be triggered by subject symptoms, if there is any concern for stroke (at scheduled visits, QVSFS results in a score > 0 or if a neurologist or a physician certified to assess neurological status suspects a stroke). It is recommended that a neurologist or physician certified to assess neurological status examines the subject, per physician’s judgment.

- If stroke is suspected or confirmed:
 - Modified Rankin Scale (see **Appendix IV: Neurologic Assessments**) must be administered by trained study personnel
 - Brain imaging study (MRI, CT) results may be collected if imaging is performed as part of routine practice or performed at time of prior stroke (at any time).
- If stroke is confirmed:
 - Results of appropriate investigations done as part of routine practice, including TEE, to determine stroke etiology, will be collected (see **Appendix I: Acronyms and Definitions** for stroke definition and etiology).

Table 4: Recommended Adjunctive Antiplatelet and Anticoagulant Medication Regimen for Successful Device Implant (per IFU)^a

Visit	Anticoagulation	Aspirin	Clopidogrel
Discharge to 45-days if patient has been on anticoagulation prior to implant for history of stroke	Yes ^d	Per institutional practice ^b	No
Discharge to 90-days	No	Yes 75-325mg	Clopidogrel ^c 75mg
>90 days	No	Indefinitely	No

^aFor subjects not implanted with an LAA occlusion device, antiplatelet and anticoagulant medications will be per physician discretion.

^bIf patient remains on anticoagulation, aspirin is not recommended

^c Prasugrel 5-10 mg QD or ticagrelor 90 mg BID may be used in place of clopidogrel in subjects unable to take clopidogrel (but may not be used with anticoagulation).

^d if patient remains on anticoagulation, cessation of anticoagulation remains at physician discretion if closure is demonstrated

	Title: WAVECREST Post Market Clinical Follow-Up (PMCF) Study	Doc. #: CHX_IP015	Rev: D
---	---	-----------------------------	------------------

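### The Protocol 6.9 discharge instruction prescribes aspirin plus clopidogrel with no exception for subjects who continue anticoagulation, in conflict with the Summary, Table 4 and 6.10

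*Protocol*

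**What the plan says.** The discharge instruction in Protocol 6.9 is unconditional: "Discharge subject on 75-325mg aspirin daily and 75mg clopidogrel". The line after it refers the reader to Table 4 for a summary of the regimen.

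Other parts of the protocol treat anticoagulated subjects differently:

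- **Summary (1.0), medication regimen and post-procedure care.** Continuing is allowed: "Patients on anticoagulants prior to implant may continue their pre-procedure regimens of anticoagulation at the discretion of the implanting physician". Clopidogrel is directed to the others: "Patients who are not on anticoagulants should receive clopidogrel 75 mg per day for 90 days post implant". Aspirin carries an explicit exception: "All patients should be maintained on 75 mg - 325 mg of aspirin per day indefinitely except those on anticoagulation".
- **Table 4, first row.** It applies to "Discharge to 45-days if patient has been on anticoagulation prior to implant for history of stroke". Its entries are Yes for anticoagulation, local practice for aspirin, and No for clopidogrel. Footnote b advises against aspirin while anticoagulation continues. Footnote c also bars the clopidogrel substitutes in combination with an anticoagulant.
- **6.10, 45-day visit.** "At the time the subject stops anticoagulation clopidogrel 75mg daily should be started and should continue until 90 days post-implant". A separate bullet tells subjects to stay on aspirin indefinitely, with no exception.
- **14.4.** It says that treated patients will take clopidogrel and aspirin for at least 90 days in line with the IFU, also with no exception.

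Section 6.7 repeats the permission to continue ("Subjects on anticoagulants prior to implant may continue their pre-procedure regimens of anticoagulation at the discretion of the implanting physician"), but under pre-procedure medications.

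**The concern.** A site that follows 6.9 to the letter adds two antiplatelet drugs to an anticoagulant that the protocol lets the subject keep. The protocol itself gives the reason to avoid this. Section 3.1 says that bleeding on NOACs rises with concomitant aspirin, and 14.4 says that aspirin with clopidogrel may carry more bleeding risk than either drug alone. Neither gives a figure for three agents together.

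The conflict also puts the investigator in a bind over compliance. Section 7.2 forbids deviations outside emergencies. For a continuing subject, withholding clopidogrel departs from 6.9 and giving it departs from the Summary. SAP 7.7 then has the sponsor classify deviations as minor or major, with no settled rule to judge against. Bleeding as such is not a component of the composite endpoint, so any excess would show mainly in the adverse-event tables.

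**Working it through.** The plan states no figure to reproduce. The check sets the texts side by side for one subject: on an anticoagulant before implant, and continuing it after discharge as the Summary allows.

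| Source | Anticoagulant | Aspirin | Clopidogrel | Agents |
|---|---|---|---|---|
| 6.9, read literally | continues | yes | yes | 1 + 1 + 1 = 3 |
| Summary | continues | no (stated exception) | no (by implication) | 1 + 0 + 0 = 1 |
| Table 4, row 1 (stroke history only) | yes | local practice; footnote b advises against | No (stated) | 1 + 0 + 0 = 1, or 1 + 1 + 0 = 2 |
| Table 4, row 2 (discharge to 90 days) | No | yes | yes | does not describe this subject |
| 6.10 | until stopped | stay on it, no exception | only once anticoagulation stops (by implication) | settles clopidogrel only |

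**Does any text resolve the conflict?**

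1. *The pointer in 6.9.* It says that Table 4 summarises the regimen. It does not say that the table overrides the bullet.
2. *Table 4 itself.* Row 1 requires prior anticoagulation for a history of stroke. A subject anticoagulated for atrial fibrillation without a previous stroke fits neither row 1 nor row 2, because row 2 has anticoagulation as No. If the site falls back on row 2, it returns to aspirin plus clopidogrel.
3. *Section 6.8.* It leaves post-implant drugs to the physician's discretion, but within the implant procedure. The 6.9 bullet has no such qualifier.
4. *The IFU.* Section 6.0 ties conduct to it, but it is not reproduced. The protocol's one direct statement of what patients take under it, in 14.4, also lacks the exception.

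**How long could it last?** The next scheduled medication review after discharge is the 45-day visit, between Day 45 − 15 = 30 and Day 45 + 15 = 60.

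**How many subjects?** The documents do not give the share of subjects on anticoagulants. The lower end is 0, if every site follows the Summary or Table 4. The only documented ceiling is enrolment, up to 65.

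**The case against.** The strongest defence is that nobody reading the whole protocol would give three agents. The line after the bullet leads to Table 4, and no row of that table combines clopidogrel with an anticoagulant. Section 6.8 allows discretion. The clopidogrel rule in 6.10 is not restricted to stroke history, so the body text covers clopidogrel for every continuing subject. Footnote b is also generally worded, although it is attached to row 1.

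Much of this stands. The practical risk is lower than the bullet alone suggests. Only Table 4 row 1 withholds clopidogrel outright; the Summary and 6.10 do so by implication. Section 6.7 concerns the period before the procedure, so the permission to continue after discharge rests on the Summary. The 6.10 aspirin bullet tells subjects to remain on aspirin, which presupposes that they already take it, so a reader should not treat it as a clear order to start aspirin in an anticoagulated subject.

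It does not remove the conflict. The bullet is the operative instruction at discharge, and nothing ranks the other texts above it. The 6.10 rule sits in the section for a visit weeks later. The one table row meant for anticoagulated subjects leaves some of them out.

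**Conclusion.** The 6.9 instruction is wrong as written and should be corrected. For a subject continuing anticoagulation it yields three antithrombotic agents, where the Summary yields one and Table 4 row 1 yields one or two. This is an internal inconsistency that affects patient safety. It rests on the wording alone and needs no numerical assumption.

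Three stronger readings are not supported:

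- *That about 23 subjects at most could be affected.* A reader might take the 65% of WAVECREST 1 patients contraindicated for anticoagulation (section 3.4) and compute (1 − 0.65) × 65 = 22.75. That share comes from a different cohort, with three device versions and sites in Europe, Australia and New Zealand. Nothing says that it carries over, so 23 is not a bound.
- *That continuing subjects will in fact receive three drugs.* The documents show what 6.9 says, not what sites do. The number is zero if they follow the Summary or Table 4.
- *That the statistical plan is affected.* No endpoint definition, sample size or confidence interval depends on this wording.

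**What to change.** - **6.9.** Make the bullet conditional. Subjects not continuing anticoagulation leave on 75-325 mg aspirin and 75 mg clopidogrel daily. Subjects continuing it receive no clopidogrel until it stops, and aspirin is not recommended in the meantime.
- **6.10.** Exempt subjects who remain on anticoagulation from the aspirin bullet.
- **14.4.** Add a matching exception, so that no unconditional statement is left behind.
- **Table 4 (optional).** Widen row 1 from stroke history to any subject continuing anticoagulation, but only if the IFU supports it, since the table is labelled as following the IFU.

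Simply declaring that Table 4 governs would not be enough. Its local-practice entry for aspirin would then override the Summary's exception, and the subjects outside row 1 would still have no rule.

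The cost is a wording amendment, submission to the ethics committees as section 12.0 requires, and notice to up to 15 sites, with an IFU check if row 1 is to be widened. No visits, procedures or data are added.

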6.11 Unscheduled Neurologic Visit

A neurologic visit may be triggered by subject symptoms, if there is any concern for stroke (at scheduled visits, QVSFS results in a score > 0 or if a neurologist or a physician certified to assess neurological status suspects a stroke). It is recommended that a neurologist or physician certified to assess neurological status examines the subject, per physician’s judgment.

- If stroke is suspected or confirmed:
 - Modified Rankin Scale (see **Appendix IV: Neurologic Assessments**) must be administered by trained study personnel
 - Brain imaging study (MRI, CT) results may be collected if imaging is performed as part of routine practice or performed at time of prior stroke (at any time).
- If stroke is confirmed:
 - Results of appropriate investigations done as part of routine practice, including TEE, to determine stroke etiology, will be collected (see **Appendix I: Acronyms and Definitions** for stroke definition and etiology).

Table 4: Recommended Adjunctive Antiplatelet and Anticoagulant Medication Regimen for Successful Device Implant (per IFU)^a

Visit	Anticoagulation	Aspirin	Clopidogrel
Discharge to 45-days if patient has been on anticoagulation prior to implant for history of stroke	Yes ^d	Per institutional practice ^b	No
Discharge to 90-days	No	Yes 75-325mg	Clopidogrel ^c 75mg
>90 days	No	Indefinitely	No

^aFor subjects not implanted with an LAA occlusion device, antiplatelet and anticoagulant medications will be per physician discretion.

^bIf patient remains on anticoagulation, aspirin is not recommended

^c Prasugrel 5-10 mg QD or ticagrelor 90 mg BID may be used in place of clopidogrel in subjects unable to take clopidogrel (but may not be used with anticoagulation).

^d if patient remains on anticoagulation, cessation of anticoagulation remains at physician discretion if closure is demonstrated

	Title: WAVECREST Post Market Clinical Follow-Up (PMCF) Study	Doc. #: CHX_IP015	Rev: D
---	---	-----------------------------	------------------

6.12 Subject Discontinuation

Participation in any clinical study is voluntary and the subject has the right to withdraw at any time without penalty or loss of benefit. Possible reasons for discontinuation may include but may not be limited to the following:

- Voluntary withdrawal
- Participation is terminated by the investigator, although the subject consented, since participation is no longer medically appropriate
- Lost-to follow-up (defined below)

If a patient decides to withdraw from the study, effort must be made to continue monitoring for adverse events even if he/she declines to continue in the study. Discuss with the patient if he/she agrees with phone follow-up only for the purpose of recording adverse events or non-invasive review of records.

Subjects who discontinue participation prematurely will be included in the ITT analysis of results (safety and performance as appropriate) but will not be replaced.

Investigators must report subject withdrawals to their respective EC as defined by their institution's procedure.

6.13 Lost-to-Follow-up (LTFU)

If a subject misses scheduled follow-up visit, and study personnel make two unsuccessful documented attempts to contact the subject, the subject will be considered lost-to-follow-up.

6.14 End of Study Participation

Subjects will be considered to have ended participation in the study when they have completed 45 day follow-up or have discontinued from the study. The appropriate CRF must be completed for the subject when:

- the subject has completed 45 day follow-up, or
- the subject has died before follow-up is complete, or
- the subject has requested to withdraw from the trial with no further contact or review of charts.

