8.8 Reporting requirements

Adverse events are reported beginning from the time the patient is enrolled until patient participation has ended.

The investigator shall inform the Sponsor of all adverse events and device deficiencies as described in table below:

Event Classification	Recording Method	Timeline
Adverse Events, including ADE	Complete appropriate CRF form	As soon as possible or as per local regulations, but no later than 2 weeks of site awareness
Serious Adverse Events, including SADE	Complete appropriate CRF form Provide all necessary documentation needed	Immediately upon awareness of the event or became aware that the event met the definition of a SAE, but no later than 72 hours
Death	Complete appropriate CRF form	Within 24 hours
UADE	Complete appropriate CRF form	Immediately upon awareness of the event, but no later than 24 hours
Device deficiencies	Complete appropriate CRF form	Within 24 hours

The investigator is responsible for informing the EC of adverse events as required by local reporting requirements.

The Sponsor will submit on regular basis (unless otherwise indicated by the EC or recommended by the Sponsor's medical safety officer) to all participating investigators an update of reported events and device deficiencies occurred at the participating study site.

The Sponsor will ensure that all events and device deficiencies are reported to the relevant authorities per country specific regulations.

The Sponsor will continue safety surveillance and safety reporting until the last follow-up visit has been performed, the subject is deceased, the subject/investigator concludes his participation in the study or the subject/investigator withdraws the subject from the study.

The Sponsor is responsible for the classification of adverse events and shall review the investigator's assessment of all adverse events.

The Sponsor will determine and document in writing their seriousness and relationship to device.

	Title: WAVECREST Post Market Clinical Follow-Up (PMCF) Study	Doc. #: CHX_IP015	Rev: D
---	---	-----------------------------	------------------

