### 7.3 Safety Endpoint

The safety endpoint for the investigation is a composite of the following through 45 days follow-up post implant:

- All-cause mortality
- Pericardial effusion requiring intervention
- Device embolization (major)
- Device thrombus
- Ischemic stroke

All safety events occur within the 45 days follow up visit window (up to Day 60) will be adjudicated by the Sponsor. The safety endpoints analysis will be based on Sponsor Assessment of Adverse Events data. No formal statistical inference will be made. The analysis will be descriptive for the ITT analysis set. The number and percentage of subjects experiencing any occurrence of the composite safety endpoint will be summarized assuming binomial distribution. The exact two-sided 95% confidence intervals will be constructed for the composite endpoint. A similar analytical approach will be performed for each component as well.

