#### 7.5 Other Safety Analysis - Adverse events (AEs)

Site reported adverse events (AEs) during the study will be coded using the Medical Dictionary for Regulatory Activities (MedDRA). The number and percentage of subjects reporting adverse events will be summarized by MedDRA system organ class and preferred term for both ITT and As-Treated analysis sets. Separate summaries will also be provided for device-related AEs and procedure-related AEs. All serious adverse events (SAEs), device-related SAEs, and procedure-related SAEs will also be summarized by system organ class and preferred term. All adverse events occurring through the 45-day (+15 days) follow-up will be summarized.

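### Event collection ends at a visit that may fall anywhere from Day 30 to Day 60, so the reported safety rate is not a clean 45-day risk

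*Protocol*

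**What the plan says.** **Visit window.** The Protocol Summary lists the visit as "45 Day Follow-up (± 15 days", and Protocol 6.10 gives the same two-sided window. A visit on Day 30 is within plan.

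**End of participation and collection.** By Protocol 6.14 subjects have "ended participation in the study when they have completed 45 day follow-up" (or when they discontinue). Protocol 8.8 states: "Adverse events are reported beginning from the time the patient is enrolled until patient participation has ended". The same section ties the sponsor's own surveillance to the visit: "The Sponsor will continue safety surveillance and safety reporting until the last follow-up visit has been performed".

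**Endpoint and analysis.** SAP 7.3 opens: "The safety endpoint for the investigation is a composite of the following through 45 days follow-up post implant". It then says: "All safety events occur within the 45 days follow up visit window (up to Day 60) will be adjudicated by the Sponsor". The composite is a number and percentage of the ITT set, treated as binomial, with an exact two-sided 95% interval. SAP 6.3 uses observed cases without imputation. Neither document sets a minimum follow-up for the denominator, a censoring rule, or a contact on or after Day 45 for someone seen early.

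**Window in the SAP.** Sections 2.1 and 3.0 give a two-sided window of 15 days. Sections 7.4 and 7.5 give only the plus side; 7.5 reads: "All adverse events occurring through the 45-day (+15 days) follow-up will be summarized".

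**The concern.** The objective is safety through 45 days. Taken together, these rules let a subject finish the study on Day 30 as a full completer. Deaths, ischemic strokes, late effusions and embolizations on Days 31-45 would then not be collected, while the subject remains in the denominator. A subject seen on Day 60 is observed for twice as long, and events from Days 46-60 may enter a rate labelled as 45-day. The percentage therefore mixes risks over different lengths of time, and the mix depends on when sites book the visit. The visit TEE, the only scheduled look for device thrombus after discharge, varies over the same 30 days.

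Only about three events are expected, so small losses are visible in the result.

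**Working it through.** **1. The plan's own figure.** Inputs from Protocol 13.1 and SAP 7.1: expected rate 5%, n = 56, exact two-sided 95% interval, upper bound below 15%, 10% drop-out. Expected events are 0.05 × 56 = 2.8, taken as 3. The exact upper bound for x events in n subjects is the 97.5th percentile of Beta(x + 1, n − x). For 3/56 = 5.4% the interval is 1.1% to 14.9%. With 3 events in 55 the upper bound is 15.1%, so 56 is the smallest n that works at 3 events. Enrollment: 56/0.9 = 62.2, rounded up to 63. Both figures reproduce.

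**2. Observation time.** A Day 30 visit leaves 15 of 45 days (33%) unobserved against the stated endpoint, or 30 of 60 days (50%) against the adjudication window. The longest and shortest in-window follow-up differ by 60/30 = 2.

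**3. Direction.** Suppose visits spread evenly over Days 30-60 (an assumption; the documents give no visit timing). Half the subjects are seen before Day 45, with a mean shortfall of 7.5 days, so 0.5 × 7.5/45 = 8.3% of person-days to Day 45 are lost. The late half gains the same number of days after Day 45. If the hazard falls with time, the earlier days carry more risk and the offset is only partial.

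**4. Expected events missed.** Let f be the share of subjects leaving at Day 30 and g the share of the risk that falls after Day 30. Both are assumptions. With N = 63 and p = 5%:

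missed = N × p × f × g; expected observed rate = p × (1 − f × g)

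| f | g | Missed events | Observed rate |
|---|---|---|---|
| 25% | 10% | 63 × 0.05 × 0.025 = 0.08 | 4.88% |
| 50% | 25% | 63 × 0.05 × 0.125 = 0.39 | 4.38% |
| 100% | 50% (extreme) | 63 × 0.05 × 0.5 = 1.58 | 2.50% |

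These rows ignore any offset from Day 46-60 events.

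**5. What one event does to the exact upper bound.**

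| n | 3 events | 4 events |
|---|---|---|
| 56 | 14.9% | 17.3% |
| 63 | 13.3% | 15.5% |
| 65 | 12.9% | 15.01% |

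The relevant n is the ITT set, about 63-65 if everyone enrolled enters it. In each row, a fourth event that goes uncollected leaves the reported bound below 15% when it should be above.

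**6. Safeguards checked.** The telephone or record follow-up in Protocol 6.12 is for subjects who withdraw. The follow-to-resolution rule in Protocol 8.1 concerns events already reported. Neither collects new events in a completer.

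**The case against.** - **The text can be read more kindly.** Protocol 2.0 says patients are followed through 45 days, and 6.14 refers to completed follow-up rather than to a visit. No sentence says that an early completer counts as event-free. This stands in part: that step is an inference from an ITT binomial percentage with no minimum-follow-up or censoring rule. But 8.8 ends sponsor surveillance at the last follow-up visit, which supports the visit-based reading. At best the text is ambiguous.
- **Little happens so late.** Most composite events are probably peri-procedural (an assumption), and Protocol 3.4 reports no safety-related events after 45 days for Version 1.3 in the WAVECREST 1 study. This limits the size. It says nothing specific about Days 31-45, and 3.4 also reports thrombus found on a follow-up TEE in 2 of 92 commercial patients, with no timing given.
- **15% is not a pass mark.** SAP 7.3 disclaims formal inference. This stands: the bound is a precision target from the sample size section.
- **The plus-15 wording is a data cutoff.** In SAP 7.4 and 7.5 it can naturally mean the same as Day 60 in 7.3. A reader might infer that the SAP assumes no visit before Day 45; sections 2.1 and 3.0, with their two-sided window, do not support that.

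**Conclusion.** The gap is real and worth closing, but its likely effect is modest. As written, time under observation varies up to two-fold among completers, and the percentage is not a clean 45-day risk. Under the moderate assumptions in the working, the expected loss is 0.08 to 0.39 events of 63, so a missed event is not the expected case. It matters because a single event decides on which side of 15% the upper bound falls.

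A reader might infer that the bias can only favour the device. The documents do not support that for a 45-day target, because SAP 7.3 adjudicates events to Day 60 and late attenders can add events from Days 46-60. The bias is strictly downward only against a Day-60 target.

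The conclusion rests on the visit-based reading of 6.14 and 8.8 and on the inference that early completers stay in the denominator. Its size rests on assumed visit and event timing.

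**What to change.** **Protocol.** Leave the visit schedule unchanged; the visit TEE is tied to anticoagulation decisions in 6.10. Amend 6.14 and 8.8 so that a subject seen before Day 45 stays in adverse event and vital status collection until a telephone contact or record review on or after Day 45. Section 6.12 already uses this method for withdrawals.

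**SAP 7.3.**
- Count composite events to one fixed day, Day 45, for the 45-day rate, and list Day 46-60 events separately. State how thrombus first seen on the scheduled TEE after Day 45 is assigned, since a bare cut would drop it; showing the rate both ways is enough.
- Report how many subjects were last observed before Day 45.
- Add a Kaplan-Meier estimate at Day 45 that censors at last contact. Do not instead restrict the composite to subjects with an event or observed to Day 45: that selects on outcome. With 3 early events in 63 and half of the 60 event-free subjects seen early, it turns 3/63 = 4.8% into 3/33 = 9.1% although nothing was missed.

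**Wording.** Reconcile the two-sided window in SAP 2.1 and 3.0 with the plus-only form in 7.4 and 7.5.

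**Cost.** One call or chart check per early attender and a few table rows; the sample size does not change. If follow-up is already complete (the SAP is dated July 2022), the SAP changes alone apply. The contact cannot recover thrombus that a later TEE would have shown, so TEE timing should be reported as a limitation.
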